APPENDIX D Text message tailoring form (Aim 1)

Personalization Tool
TXTXT Intervention

[INSERT DIMAGI web address here]

1. What is the name of your cell phone provider?

- 1. AT&T
- 2. Boost Mobile
- 3. Cricket
- 4. MetroPCS
- 5. Sprint
- 6. Tello
- 7. T-mobile
- 8. TracFone
- 9 - US
- Cellular 10 -
- US Mobile11
- Verizon
- 12- Virgin
- 97 – Other

1a. If Other, specify: _____

2. What is your cell phone number? ----- _____

[NOTE: Counsel Participant to text “STOP” if they want to stop receiving texts, “START” to receive them again]

3. What language do you want to receive text

messages in? 1- English 2- Spanish

For first medication dose:

4. What time would you like to receive the text message reminder to take your medication?

____ : ____ AM/PM

4a. What do you want the text message reminder to say? (Limit 160 characters)

Note to interviewer: Does chosen text message disclose status? If so, discuss with participant and suggest alternate options.

4b. Fifteen minutes after you receive the first text, we will send you another text that will ask you to respond (via text) once you have taken your medication. What do you want this text message to say?

+ respond “1:Yes” if you took your medication, “2: No” if you did not

If a second medication dose:

Note to interviewer: If only one medication dose, skip to END

5. Time : ____ AM/PM

If a third medication dose:

Note to interviewer: If only two medication doses, skip to END

6. Time : ____ AM/PM

APPENDIX E Encouraging messages (Aim 1)

Encouraging Messages

The following is a list of encouraging messages to be programmed for automated reply.

Replies for “Yes” Taken Meds

1. Great job!
2. Way to go!
3. Keep it up!
4. Good work!
5. You rock!
6. Nice!
7. That's great!
8. Sweet!
9. Woo who!
10. YEAH!!
11. Good work!
12. I'm so glad to hear that!
13. Yay!
14. That's wonderful!
15. That's amazing!
16. You're awesome!
17. That is excellent
18. You should be proud!
19. Fabulous!
20. That's fantastic!
21. Super duper
22. You're a rock star
23. high five!
24. thumbs up!
25. Hurray!
26. Woot! Woot!
27. Spectacular!
28. Splendid
29. You are so magical
30. Tremendous!
31. Marvelous
32. You're extraordinary
33. YAS!
34. Awesome!
35. Killing it!
36. You got this!

Replies for “No” Taken Meds

1. You can do it!
2. Go for it, you still have time!
3. Ooops! Now!
4. Uh oh, but you still have time.
5. Come on! You got this!
6. Oh no! You got this, don’t quit!
7. Shoot! Better a little late than never.
8. Shucks, you still have time.
9. You’ve got it, you still have time!
10. Try, try again
11. Just do it!
12. Dang! Now!
13. Drat, you still got this!
14. Bummer! Don’t quit!
15. Fooey, do it now!
16. Blast. Do it now!
17. Aw crud. Better late, than never.
18. Darn! You still have time!
19. Dangit!
20. It is what it is. You got this!

Appointment Reminder messages

1. You have a visit coming up on [DATE/time]
2. Don’t forget your visit on [DATE/time]
3. See you on [DATE/time] for your visit
4. See ya soon! [DATE/time]

5. Your scheduled visit is

[DATE/time]Medication Refill

reminder

1. Pick up your vitamins [DATE]
2. Thumbs up for pick-up [DATE]
3. Just a reminder to get your things [DATE]
4. You have a pick up [DATE]
5. Package for you [DATE]

APPENDIX F Measures via CASI (Aim 1)

BARRIERS AND FACILITATORS OF ADHERENCE

People may miss taking their HIV medications for various reasons. Here is a list of possible reasons why you may have missed taking any HIV medication in the past month.

In the past month, how often have you missed taking your medications because you:

Please circle only one response for each question

		Never	Rarely	Sometimes	Often
1	Were away from home?	0	1	2	3
2	Were busy with other things?	0	1	2	3
3	Simply forgot?	0	1	2	3
4	Had too many pills to take?	0	1	2	3
5	Wanted to avoid the side effects?	0	1	2	3
6	Did not want others to notice you taking medication?	0	1	2	3
7	Had a change in daily routine?	0	1	2	3
8	Felt like the drug was toxic/harmful?	0	1	2	3
9	Fell asleep/slept through dose time?	0	1	2	3
10	Felt sick or ill?	0	1	2	3
11	Felt depressed/ overwhelmed?	0	1	2	3
12	Had problem taking pills at specified times (with meals, on empty stomach, etc.)?	0	1	2	3
13	Ran out of pills?	0	1	2	3
14	Felt good?	0	1	2	3
15	Do you use a pillbox to help you remember to take your medications?		1 Yes		0 No

1. Are there circumstances in your life that make taking your medications on a regular basis more difficult?

1.1 Yes

0 No (SKIP to Q18)

1. What are the circumstances in your life that make taking your medications

2. difficult?(Describe in brief)

2. Are there circumstances in your life that make taking your medications on a regular basis easier?

1.1 Yes 0 No (SKIP to next measure)

1. What are the circumstances in your life that make taking your medications easier?

DEMOGRAPHIC QUESTIONNAIRE

DEM1. What is your date of birth? ____/____/____ [mm/dd/yyyy]

DEM2. Which of the following best represents how you think of yourself?

- 1-Gay (lesbian or gay)
- 2 -Straight, this is not gay (or lesbian or gay)
- 3 -Bisexual
- 97 -Something else

DEM2a. If =97, specify_____

DEM3. What is your sex assigned at birth/biological sex?

- 1. – Male
- 2. – Female
- 97 – Something else

.DEM3a. If =97, specify:_____

DEM4. How do you describe your gender identity?

- 1. Male
- 2. Female
 - 3. Transgender woman
 - 4. 4- Transgender man

1. Non binary

2. Gender queer/Gender expansive

97-Something else

DEM4a. If =97, specify:_____

DEM5. Are you Hispanic or Latino/a?

- 1- Yes
- 0- No

DEM5a. (If =1), Are you: Mexican, Mexican American, or Chicano/a; Puerto Rican; Cuban; or another category of Spanish/Hispanic/Latino/a that we have not mentioned?

1. - Yes, Mexican, Mexican American, Chicano/a
2. - Yes, Puerto Rican, Puerto Rican American
- 3 - Yes, Cuban, Cuban American
- 97 – Yes, Other Spanish/Hispanic/Latina

DEM5b. If =97, specify: _____

DEM6. What do you consider to be your primary race or ethnic background (check all that apply)?

1. – White
2. – Black/African American
- 3 – Asian
1. – American Indian/Alaskan Native
2. – Native Hawaiian or Other Pacific Islander

DEM7. What is your highest level of education?

- 1 - Less than 8th grade
- 2 - Completed 8th grade, no high school
1. - Some high school (completed some grades 9th-12th, but no diploma or GED)
 2. - High school diploma or GED
 3. -Trade School Certificate
1. - Some college
 2. - Undergraduate degree
 3. -Some graduate school
 4. -Graduate degree

DEM8. Are you currently a student?

1-Yes
0-No

DEM9. What was your household income over the past 12 months from all sources before taxes?
Household income refers to the total amount of money from all people living in the household.

1 - Less than
\$10,000
2 -\$10,000
- \$19,999
3 - \$20,000 – \$29,999
4 - \$30,000 - \$39,999
5 - \$40,000 - \$49,999
6 - \$50,000 - \$59,999
7 - \$60,000 - \$69,999
8 - \$70,000 - \$79,999

9 - \$80,000 or more

77- Don't know

DEM10. Including yourself, how many people depend on this income?__

DEM11. Do your sources of income or support include any of the following? Your sources of income may include public assistance and non-traditional jobs. Check all that apply:

- 1- Traditional job (retail, office, restaurant; paid in regular intervals)
- 2- Day labor (paid by the day, no promise of additional work)
- 3- Selling or dealing drugs

- 1. Sex work, survival sex or prostitution
 - 2. Street income (panhandling, boosting or stealing)
 - 5- Unemployment benefits
 - 6- SSI or disability
 - 7- Food stamps
- 1. Income provided by a partner
 - 2. Income provided by other family members
 - 10- Income provided by a "sugar daddy"
- 1. No income
 - 2. Student stipend
 - 13 None of the Above
 - 14 Under-the-table ("off the books," not reported to the government by the employer)
 - 97- Something else

DEM11a. If =97, specify:__

DEM12. In your lifetime, have you ever been homeless at all? That is, you slept in a shelter for homeless people, on the streets, at a friend or relative's house for a few nights or weeks, or another place not intended for sleeping.

1 – Yes

0 – No (skip to DEM26)

DEM12a. Approximately how many total nights have you not had a regular place to stay during your lifetime?
____years and ____ nights

DEM12b. In the past 3 months, were you homeless at any time?

1 – Yes
0 – No

DEM13. What is your zip code where you currently live? _____

DEM14. Which of the following best describes your current living situation? By current living situation we mean where you have been staying during the past seven days.

1. Your own place, a room, apartment, or house that is your home
2. Temporarily doubled up with others, in someone else's house, apartment, or room
3. A temporary or transitional housing program
4. An SRO, that is a "single room occupancy" hotel or motel
5. In a shelter for homeless people
6. In jail, prison, or a halfway house
7. In drug treatment, a detox unit, or drug program housing
8. In a hospital, nursing home, or hospice
9. In an abandoned building, a public place like a bus station, a store or another place not intended for sleeping
10. On the street or anywhere outside such as a park, under a bridge, or in a campground
- 97- Something else

DEM14a. If =97, specify: _____

DEM15. How long have you lived at your current place (in # of years and # of months)? _____

DEM16. Are you currently involved in a committed relationship with someone who you consider your boyfriend/girlfriend, spouse, or domestic partner?

1. - Yes
- 0- No (skip to END of DEM)

DEM16a. How long have you been in this relationship? (If you are currently involved in more than one relationship, select the most significant one).

1. - Less than a month
2. - One month to six months
3. - More than six months to a year

- 4. - More than a year to three years
- 5 - More than three years

HIV Medication Taking Self-efficacy Scale

Indicate on the following scale how confident you are in the following:

1. That you can keep a clinic appointment

2. That you can follow your overall treatment regimen

3. That you can follow a plan for taking HIV medication

4. That you can take HIV medication with correct intervals

5. That you can take the correct dose

6. That you can take HIV medication at work

7. That you can take HIV medication on a weekday

8. That you can take HIV medication on a weekend

9. That you can take HIV medication at social outing

10. That you can take HIV medication at a party

11. That you can take HIV medication at a planned event

12. That you can take HIV medication at an unplanned event

13. That you can take HIV medication at travel

1. That you can take HIV medication when you feel well

2. That you can take HIV medication when you feel ill

3. That you can take HIV medication when you are having medication sideeffects

4. That you can take HIV medication when you are having in a crisis

Outcome expectancy (OE)

5. That taking HIV medication will improve your health

19. That taking HIV medication will improve quality of life

Not
Confident

Totally
Confident

1 2 3 4 5 6 7 8 9 10

1. That taking HIV medication will improve function ability

Not
Confident

Totally
Confident

1 2 3 4 5 6 7 8 9 10

2. That taking HIV medication will allow for a long life

Not
Confident

Totally
Confident

1 2 3 4 5 6 7 8 9 10

3. That taking HIV medication will allow you to lead a near normal life

Not
Confident

Totally
Confident

1 2 3 4 5 6 7 8 9 10

4. That taking HIV medication will decrease HIV related symptoms

Not
Confident

Totally
Confident

1 2 3 4 5 6 7 8 9 10

5. That taking HIV medication will decrease viral load

Not
Confident

Totally
Confident

1 2 3 4 5 6 7 8 9 10

6. That taking HIV medication will increase T-cell count

7. That taking HIV medication will prevent hospitalization

HIV Medication Adherence

This questionnaire asks you how often you take your HIV medication. Some people get busy and forget to take their HIV medications or forget to carry their medications with them. Other times people find it hard to take their medications like their doctor told them to, such as “with food” or “on an empty stomach.” Other people decide to skip medications to avoid side effects (like feeling sick to your stomach) or to just not take their medications that day. It’s important for us to understand what people with HIV are really doing with their medications. For these questions, please report what you are actually doing. Don’t worry about it if you don’t take all of your medicine. We want to know what is really happening, not what you think we “want to hear.”

1. Do any of your HIV medications have special instructions, such as “take with food” or “on an empty stomach” or “with plenty of fluids?”

1 Yes 2 No (If NO, skip to question #2)

1. IF YES, how often did you follow those special instructions over the last four days?

Never	Some of the time	About half of the time	Most of the time	All of the time
 0	 1	 2	 3	 4

2. Some people find that they forget to take their pills on the weekend days. Did you miss any of your HIV medications last weekend—last Friday, Saturday or Sunday?

1 Yes 2 No

3. During the past 4 days, on how many days have you missed taking all doses of your HIV medications?

1. none
2. one day
3. two days
4. three days
5. four days

Now I'm going to ask you about the last 30 days. For all of your current HIV medications, what percent time (%) from 0 to 100 did you take your medication as prescribed in the last 30 days?

0% time would mean, "NONE of the time," 50% time would mean HALF of the time and 100% would mean ALL of the time. Numbers in-between would mean amounts between NONE and ALL of the time.

6. Please put an "X" on the line below at the point showing your best guess about how much you have taken these drugs in the **last 30 days**. [display VAS SCALE GRAPHIC].

NONE

ALL

The picture can't be displayed.

Treatment acceptability measure

Adapted from: <https://link.springer.com/content/pdf/10.1007/bf00960091.pdf>

How effective do you think this program (TXTXT) is might be?	1= very ineffective 2 3 4 5 6 7= very effective
How acceptable do you find the program (TXTXT) to be?	1= very unacceptable 2 3 4 5 6 7= very acceptable
How likely do you think it is that this program (TXTXT) will have negative impact?	1= very unlikely 2 3 4 5 6 7= very likely

TXTXT Acceptability Survey

1. Did you receive text message reminders on the days and times you requested them?

1- Yes 2- No

2. How often did you read the text messages?

4- Always 3- Often 2- Sometimes 1- Never

3. How often did you find the text messages intrusive or bothersome?

4- Always 3- Often 2- Sometimes 1- Never

4. Did anyone find out you were HIV+ because you received the text messages?

1- Yes 2- No

5. How often did you respond “yes” to the text indicating you took your medication, when you really didn’t take them?

4- Always 3- Often 2- Sometimes 1- Never

The goal of the TXTXT intervention is to support daily medication adherence and ultimately improve viral suppression.

6. Thinking about your experience with the TXTXT intervention, what worked best? What would you like to see changed?

7. Do you have any other suggestions for improving the TXTXT intervention?

Client Satisfaction Questionnaire (CSQ-8)

Please help us improve the text messaging intervention by answering some questions about your experiences. We are interested in your honest opinion, whether they are positive or negative. Please answer all of the questions.

1. How would you rate the quality of your experience with the text message reminders?

4	3	2	1
Excellent	Good	Fair	Poor

2. Did you get the kind of text message reminder experience that you wanted?

4	3	2	1
No, definitely not	No, not really	Yes, generally	Yes, definitely

3. To what extent have the text messaging reminders met your needs?

4	3	2	1
Almost all of my needs have been met	Most of my needs have been met	Only a few of my needs have been met	None of my needs have been met

4. If a friend were in need of similar help taking their medication, would you recommend the text reminder intervention to him or her?

4	3	2	1
No, definitely not	No, not really	Yes, generally	Yes, definitely

5. How satisfied are you with the amount of help you have received with the reminders?

4	3	2	1
Quite dissatisfied	Indifferent or mildly dissatisfied	Mostly satisfied	Very satisfied

6. Have the text messaging reminders helped you to take your medication?

4	3	2	1
---	---	---	---

Yes, they helped a great deal

Yes, they helped somewhat

No, they really didn't help

No, they seemed to make things worse

7. In an overall, general sense, how satisfied are you with the text message reminder intervention?

4	3	2	1
Very satisfied	Mostly satisfied	Indifferent or mildly dissatisfied	Quite dissatisfied

8. If you were to seek help again, would you want to receive the text message reminders?

4	3	2	1
No, definitely not	No, not really	Yes, generally	Yes, definitely

1. likert scale: Not at all, slightly, somewhat, mostly, very

Intervention Utility Questionnaire; modified from:

<https://www.ncbi.nlm.nih.gov/pmc/articles/PMC2954428/#!po=76.6667>

1. To what extent did you find the TXTXT intervention easy to use?
2. To what extent did you find the TXTXT intervention convenient to use?
3. To what extent did you find the TXTXT intervention understandable?
4. To what extent did you find the TXTXT intervention useful?
5. To what extent did you find the TXTXT intervention enjoyable?
6. To what extent did you find the TXTXT intervention consistent with other adherence strategies?
7. To what extent did you find the TXTXT intervention suitable for helping you remember to take your medication?
8. To what extent did you find the TXTXT intervention generally effective?
9. To what extent did you find the TXTXT intervention effective as a long term support for adherence?

FIDELITY CHECKLIST

PARTICIPANT NAME: _____ INTERVIEWER INITIALS: |_____|____|

VISIT DATE: |_____|-|_____|-|_____|-|_____|-|_____| **VISIT TYPE (CIRCLE):** Initial | 3M | 6M

Month Day Year

1. Completed study assessment? Yes No
1. Completed adherence counseling (initial visit only)? Yes No N/A
1. Completed personalization form (or updated at FU)? Yes No
1. Next appointment scheduled (initial, 3M only)? Yes No N/A
o Date ____ / ____ / ____ Time ____ : ____ am/pm
1. Updated contact information? Yes No N/A

Comments:

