In this study we propose to use implementation science (IS) to scale up and evaluate the TXTXT evidence-based intervention (EBI) as an effective strategy to increase ART adherence and retention in HIV care, ultimately leading to a suppression of viral load among Black/African American, Hispanic/Latino and other racial/ethnic minority youth and young adults living with HIV (YYALH) participating in the intervention. We hypothesize that those who complete the TXTXT intervention will demonstrate a clinically meaningful increase in ART adherence, viral suppression, and sustained retention in care. Additionally, we hypothesize that the implementation of TXTXT will reach $\geq 80\%$ of the intended participants, will be fully adopted by $\geq 80\%$ of clinic partners, and will achieve $\geq 90\%$ ratings of satisfaction and acceptability. We will use mixed methods to complete our study aims: 1) determine the real-world efficacy of a regional scale up of an EBI – TXTXT -among poorly adherent racial/ethnicity minority YYALH, aged 16-35 years, on our primary outcomes: adherence and viral load suppression at 3-month post initiation of the intervention; and secondary outcome: retention in HIV care at 12-months post baseline, and 2) apply the Consolidated Framework for Implementation Research (CFIR) to describe the implementation process and identify barriers and facilitators needed to be addressed; and measure implementation outcomes of the TXTXT intervention using the RE-AIM framework (Reach, Efficacy, Adoption, Implementation, Maintenance). We will conduct a cluster randomized controlled trial to evaluate the intervention effectiveness (i.e., ART adherence, viral load suppression) at 3-months post-initiation of the intervention. Twelve clinic sites with the ability to enroll up to 50 participants at each site (N=600 participants total) will be trained to administer the TXTXT intervention. Sites will be randomized to either start the intervention immediately (i.e., intervention arm) or waitlisted to start at 3 months post baseline (i.e., comparison arm). In the comparison arm, the study will compare pre-post differences in adherence and viral suppression at 6 months post baseline. Last, we will evaluate retention in HIV care and sustained impact of the intervention at 12 months post baseline for all study participants.

RESEARCH TEAM

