yet?" and "Don't forget!" The SMS platform is bi-directional and has an automated response system, so the participant is able to answer "1=yes" or "2=no" in response (press 1 or 2). When participants respond affirmatively, they will receive an encouraging message such as, "Great job!" However, when they respond with a "no" they will receive an acknowledging and encouraging message such as "You can do it!" (Appendix E).

Participants will be asked to complete a self-administered online survey at baseline, 3 months and 6 months post baseline. The survey will be hosted on REDCap and can be taken on a computer, tablet, or mobile phone. Participants will have the option of completing the survey remotely or coming to the clinic and taking the survey on-site (at a computer or tablet provided by the clinic). The online survey will be taken by both the intervention and comparison arm. The survey will measure demographics, self-reported ART adherence, HIV medication self-efficacy, barriers and facilitators of adherence, acceptability of TXTXT, and satisfaction (Appendix F). The survey CASI will be pilot tested with a small number of participants and adjusted as needed. Participants will also be asked to consent to release of specific EMR data to include viral load and attendance at HIV care visits.

At all study visits, staff will use the Fidelity Checklist to structure the visit and make sure that all procedures are followed (Appendix G). All study visits reflect the following general structure:

1. Complete intervention assessment
2. Complete standard-of care adherence counseling
3. Complete TXTXT Personalization form
4. Enter information into Dimagi platform (see Dimagi training, Appendix B)
5. Schedule date of next appointment
6. Build general rapport
7. Thank them for participation

As part of the initial visit, basic ART adherence education should be provided, based on the practices and/or protocols at each site. For example, if a site does not have a standard practice for adherence counseling, at a minimum staff should review:

1. The current list of medications prescribed to each participant and how each medication should be taken (make sure they know how to take their prescribed medication).
2. In addition, basic facts on the importance of adherence should be reviewed with each participant, such as those described here:
<https://aidsinfo.nih.gov/understanding-hiv-aids/fact-sheets/21/54/hiv-medication-adherence>

Retention

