In order to assess feasibility, acceptability and satisfaction of the intervention we will use descriptive statistics using a combination of objective (e.g., rates of participation, intervention completion) and subjective measures (e.g., reported satisfaction, acceptability). In order to characterize adherence and retention in care throughout the course of the study, Kaplan-Meier survival curves will be used to measure time to adherence and retention, and Cox proportional hazard ratios will be used to assess whether individual-level factors are associated with shorter mean time to outcome. To measure reach of the intended participants, we will compare the study sample to those available in the sampling frame (proportion of those enrolled to those eligible). To measure adoption of clinic partners, we will evaluate the number of clinic partners who propose to continue with text messaging as adherence support post study (proportion of clinics who propose to continue TXTXT post study to total clinics). Satisfaction and acceptability will be measured by standard quantitative scales, summary total scores will be evaluated to determine whether or not ≥90% ratings were achieved.

Outcome definitions

Medication adherence: greater than or equal to 90% on self-reported visual analog scaler (non-adherence categorized at less than 90%)

Retention in care³³: two visits 90 days apart in the past year will be considered retained in HIV care

Viral suppression³⁴: VL < 200 copies/mL will be considered virally suppressed

Sample size, power calculation, and clinic scale up

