Dimagi Commcare is HIPAA-compliant; no health information will be stored in the Dimagi platform. This is a secure system and will be further protected by login credentials for limited access, to protect confidentiality. Staff will only access Dimagi to register participants for text messages; [name], the data manager ([name]), and Co-Investigator [name] will have access to the SMS data (number of texts received; number responded) via encrypted, password protected files.

DATA AND SAFETY MONITORING PLAN

Lurie Children's ([name], supervised by [name]) will be responsible for computerized survey programming, data capture, management and analysis. All study information will be identified

through the PID on all forms and computerized files. Computer data files will never contain any identifying information and are encrypted prior to transfer between study sites. All SMS-related data will be securely stored by Dimagi per their HIPAA-compliant privacy policy.

Data entered into the Stata databases will not include any identifying information. Only authorized users with a password will be able to open up the computerized survey, and only those with administrative privileges (i.e., login name and password) will be able to access data. The study staff will use a password to gain access to the software in order to administer it to a participant, but they will have no ability to access the saved data. The Data Manager will set up the database, check data quality, and prepare the data for use. In addition, the database, data structure, and data quality will be routinely reviewed by [name]. Data quality will be examined before statistical analyses are conducted, including examination of missing data, assessment of distributional assumptions, and identification of outliers.

All proposed staff have participated in the NIH required trainings for conduct of studies that involve human subjects, and any future study staff will do so upon hiring. Training for all staff includes (but is not limited to) Human Subjects, Informed Consent, Good Clinical Practice, Quality Management, and Confidentiality and Reporting of Adverse Events. If any study staff discovers an untreated condition in a patient (e.g., onset of physical or mental health condition), they will refer participants to appropriate treatment immediately.

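### The CSQ-8 satisfaction form reverses its coding on four of eight items with no stated reversal rule; summed as printed, fully satisfied and fully dissatisfied respondents both total 20 of 32

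*Combined protocol and SAP*

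**What the plan says.** The Protocol Summary hypothesises that implementation will achieve at least 90% "ratings of satisfaction and acceptability". The Aim 1 section Data Analysis Plan and Variables says these will be measured by standard quantitative scales and that "summary total scores will be evaluated to determine whether or not ≥90% ratings were achieved".

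The CSQ-8, in Appendix F, is the satisfaction scale by name. All eight items carry the code row 4-3-2-1 from left to right, but the labels beneath do not all run the same way:

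- **4 is the most favourable answer:** items 1, 3, 6 and 7. Item 7 asks "In an overall, general sense, how satisfied are you with the text message reminder intervention" and codes *Very satisfied* as 4.
- **4 is the least favourable answer:** items 2, 4, 5 and 8. Item 5 asks "How satisfied are you with the amount of help you have received with the reminders" and codes *Quite dissatisfied* as 4. Item 2 ("Did you get the kind of text message reminder experience that you wanted"), item 4 and item 8 ("If you were to seek help again, would you want to receive the text message reminders") all code *No, definitely not* as 4.

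No section gives a scoring key, a recoding step or a reversal rule. Two general safeguards are stated. On the survey, Procedures for Recruitment and Informed Consent says: "The survey CASI will be pilot tested with a small number of participants and adjusted as needed". The Data and Safety Monitoring Plan requires data-quality review before analysis, "including examination of missing data, assessment of distributional assumptions, and identification of outliers". Neither mentions scoring direction.

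**The concern.** A summary total has meaning only if every item points the same way. Here four items point one way and four the other. Items 5 and 7 show this most clearly: with the same four labels, *Quite dissatisfied* is 4 on one and 1 on the other. If the printed codes are stored and added, the two halves of the scale cancel. The total then measures the difference between the halves instead of satisfaction.

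At stake is the satisfaction half of a stated implementation hypothesis, which could be reported as failed in a sample that was fully satisfied. Every stored value would be a legitimate 1 to 4, so range and outlier checks on single items would not flag the problem.

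The target is also loosely defined. The 90% could be a mean percentage of the maximum, a percentage of the rescaled range, or the share of participants above some cut.

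**Working it through.** The documents give no CSQ-8 total, range or worked score, so there is no plan figure to reproduce. The inputs are the codes and labels in Appendix F.

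**Code printed for each level of satisfaction**

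| Level, same on every item | Item 1 | 2 | 3 | 4 | 5 | 6 | 7 | 8 | Printed total | Recoded total |
|---|---|---|---|---|---|---|---|---|---|---|
| Best | 4 | 1 | 4 | 1 | 1 | 4 | 4 | 1 | 20 | 32 |
| Second | 3 | 2 | 3 | 2 | 2 | 3 | 3 | 2 | 20 | 24 |
| Third | 2 | 3 | 2 | 3 | 3 | 2 | 2 | 3 | 20 | 16 |
| Worst | 1 | 4 | 1 | 4 | 4 | 1 | 1 | 4 | 20 | 8 |

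The recoded total replaces the code on items 2, 4, 5 and 8 by 5 minus the code.

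**As percentages.** 20/32 = 62.5% of the maximum; (20 − 8)/(32 − 8) = 12/24 = 50% of the range.

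**General form.** Score each item 1 to 4 in the favourable direction. Let A be the sum over items 1, 3, 6 and 7, and B the sum over items 2, 4, 5 and 8.

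- Correct total = A + B.
- Printed total = A + (4 × 5 − B) = 20 + A − B.

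If the favourable-direction mean is m on every item, the printed mean total is 4m + 4(5 − m) = 20 whatever m is, while the recoded mean total is 8m. At m = 3.6 the recoded mean is 28.8, exactly 90% of 32; the printed mean is still 20.

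**Respondents who are not uniform.** A 90% cut is 0.9 × 32 = 28.8, or 8 + 0.9 × 24 = 29.6 on the rescaled range. Enumerating all answer patterns, 165 have a correct total of 29 or more. Their printed totals lie between 17 and 23, so none reaches 28.8. To reach 29 on printed codes a respondent needs A − B of at least 9, out of a possible 16 − 4 = 12. That means praising the intervention on one half of the form and rejecting it on the other.

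**If 90% means a share of participants above a cut.** Fully satisfied and fully dissatisfied samples give the same answer: both 0% if the cut is above 20, both 100% if it is 20 or below.

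**Sensitivity to item 6.** Its labels are detached from the code row in the text available and are read here in the order printed.

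- Item 6 omitted: best = 20 − 4 = 16 of 28 (57.1%); worst = 20 − 1 = 19 of 28 (67.9%).
- Item 6 coded the other way: best = 16 + 1 = 17 of 32 (53.1%); worst = 19 + 4 = 23 of 32 (71.9%).

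In both cases dissatisfied respondents score higher than satisfied ones.

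**The case against.** The strongest reply is that the harm depends on something the documents do not show. The survey runs in REDCap, Appendix F reads in places like a working draft, and the survey is to be piloted and adjusted. The stored values may differ from the printed row. This stands: the label conflict is certain from the form, but the 20 of 32 result is conditional.

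Second, mixed item direction is not an error if the reversed items are recoded, and calling the scales standard may imply the instrument's usual scoring. That is fair as to intent. But no such scoring is written down, and the two items with identical labels cannot both enter an unreversed total correctly.

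Third, exact equality at 20 holds for respondents at one level throughout, or for samples with equal item means, and it relies on the reading of item 6. This also stands. The other readings of item 6 do not rescue the score, and the enumeration shows that highly satisfied respondents with mixed answers still fall well short of 90%.

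Fourth, the analysis section does not name the CSQ-8 as the scale that decides the target. That link is an inference from its name and content, since Appendix F also holds an acceptability survey and a utility questionnaire.

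Finally, totals clustered near 20, with items 5 and 7 pulling in opposite directions, might be noticed when distributions are examined. That makes an undetected error less likely but does not replace a scoring rule.

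**Conclusion.** The concern holds. The form contradicts itself on four of eight items, no reversal rule is stated, and the 90% target is undefined; these three facts need no assumption. If the printed codes are stored and summed, and item 6 is read in print order, every uniform respondent totals 20 of 32 (62.5% of the maximum, 50% of the range), against 32 for fully satisfied and 8 for fully dissatisfied after recoding. The satisfaction hypothesis could then be reported as failed in a fully satisfied sample.

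The reach is limited. Only the satisfaction outcome, and possibly acceptability, is affected; adherence, viral suppression and retention are not. The outcome can be recovered from item-level data. It should be corrected before the satisfaction outcome is analysed, but it does not threaten the trial's main results.

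**What to change.** 1. Compare the REDCap data dictionary with the printed CSQ-8.
2. If the stored codes match the form, recode items 2, 4, 5 and 8 as 5 minus the code before summing. If no responses exist yet, correct the printed codes on those items to 1-2-3-4 instead. Do one or the other, not both.
3. Write the scoring rule into the analysis plan and name the CSQ-8 as the satisfaction scale, if that is the intention.
4. Apply the 90% target to the recoded total, and say whether it means mean percentage of the maximum or the share of participants above a named cut.
5. State which items form the acceptability total. If the three treatment-acceptability items are to be summed (an assumption; the plan does not say so), reverse the third, on negative impact, as 8 minus the code. It is labelled correctly but worded negatively, so without reversal the most favourable response is 7 + 7 + 1 = 15 of 21 (71.4%).

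The cost is a data-dictionary check, one recode line or a form correction, and a short addition to the plan. It works on responses already collected, provided item-level answers are kept.
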